Secondary outcomes: 1) Days using opioids, and days injecting drugs per 28 days prior to each major assessment point (weeks 4, 8, 12, and 24 post randomization) (longitudinal, continuous); 2) Urine toxicology-confirmed abstinent (urine toxicology negative for illicit opioids, and self-report negative over past 7 (at week 1) or 30 days (weeks 4, 8, 12, 24) (longitudinal, binary); 3) Completion of the prescribed course of antimicrobial therapy (binary), Re-hospitalization for infection by week 12 (binary); 4) Days using other drugs/alcohol per 28 days prior to each assessment (longitudinal, continuous); 5) Urine toxicology positive for non-opioid drugs (longitudinal, binary); 6) Social functioning and quality of life (WHOQOL-Bref) at 12 and 24 weeks after randomization (longitudinal, continuous); 7) Modified PEG Pain Scale at each assessment (Longitudinal, continuous) 8) HIV risk behaviors—days in past 28 days of vaginal or anal sex without a condom at weeks 4, 8, 12, 24 (longitudinal, continuous); 8) Any needle sharing in past 28 days (longitudinal, binary); 9) Treatment satisfaction (via the TSR)¹² at 12 and 24 weeks (longitudinal, continuous); 10) Discharge “against medical advice” (binary); 11) Cure of index infection (binary); 12) HCV cure or link to treatment (binary); 13) HIV Viral suppression (Viral Load < 200 copies), if HIV positive (binary); 14) overall hospitalization by week 12; 15) ED visits by week 12; 16) Serious adverse events (SAFETEE and non-fatal and fatal overdose) (binary).

Additional variables: *Covariates, primary and secondary analyses: Stratification factors:* Site (3 sites: YNHH; Columbia/Penn State Hershey; South Carolina/Greenville) will be included as a fixed effect in all analyses. *Covariates:* In general, the baseline score for each outcome measure (where applicable) will be included as a covariate in outcome analyses. *Moderators:* A range of baseline moderator variables will be explored including 1) Demographic characteristics (gender, age, ethnicity, living situation (domiciled vs homeless); 2) Modified Pain PEG scores at baseline (continuous) 3) Evidence of fentanyl use at admission (urine toxicology, self-report) (binary); 4) Other substance use at baseline (any cannabis, any stimulant, any heavy drinking days; binary); 5) Probable major depression at baseline (binary based on PHQ score); 5) Type of infection (endocarditis/ osteomyelitis/bacteremia/ cellulitis/ etc.). *Mediators:* 1) Social functioning

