(WHOQOL-Bref); continuous); 2) Opioid craving (continuous); 3) Pain (Modified PEG scores; continuous).

Intent to Treat, Dropouts, and Missing Data: All analyses will be on the Intent-to-treat (ITT) sample, i.e., all randomized subjects (N=200) according to the treatment arm to which they were assigned. For the primary outcome and secondary outcomes related to treatment engagement, any patients lost to follow-up will be assumed not to be enrolled in treatment nor to have completed the antimicrobial course. Loss to follow-up will be minimized through collection of extensive locator information at baseline and proactive outreach, as described above. For the secondary outcomes related to substance use, missing data (patients who cannot be located) will be assumed to be opioid positive (not abstinent), a typical assumption which is reasonable based on the high rate of relapse among patients with OUD who discontinue medication treatment.^{14,44-46} For other secondary outcomes, missing data will be treated as missing at random. Longitudinal mixed effects models do not require complete data to provide estimates of the outcome, and the estimates are considered valid under the assumption that the data are missing at random.⁴⁷ We will additionally perform sensitivity analysis for the secondary outcomes to examine the influence on the outcomes of dropout and missing data by performing several imputation methods, for instance imputing missing weeks as all abstinent or all non-abstinent. Comparison of the inferences from assuming various models for the missingness provides a measure of the validity of the efficacy estimate from the initial model.

Significance Testing and Preliminary Analyses: All tests for main effects will be performed at two-sided significance level of 5%. Before performing specific analyses, we will examine the distributions of outcome measures and covariates and investigate for outliers. The distributions of continuous variables will be checked for normality, and transformed, if necessary. Distribution of demographic and other baseline variables will be examined and described in terms of means, standard deviations, proportions and 95% confidence intervals. Covariates will be examined for association with treatment outcome. Covariates associated with treatment outcome will be adjusted for in models used to test study hypotheses.

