Primary outcome Statistical Model: *Hypothesis:* Assignment to the ID/LAB arm (OUD managed directly by the ID or hospitalist team with long acting injection buprenorphine) will promote greater enrollment in effective medication treatment for OUD (MOUD) at 12 weeks after randomization, compared to TAU. The effect of randomization to the ID/LAB arm compared to the TAU arm will be estimated using logistic regression with the binary outcome of enrollment (yes/no) modeled as a function of treatment condition (ID/LAB vs TAU), with Site as a fixed effect, and covariates/moderators as listed above under 'Additional Variables'. The odds ratio of the treatment term and its confidence limits will estimate the treatment effect. The raw retention rates in each treatment group and rate differences will be computed for descriptive purposes.

Power Analysis: Previous studies of buprenorphine initiation in an Emergency Department⁴² and on a medical inpatient service,⁴³ yielded rates of post-discharge buprenorphine maintenance treatment in the 70% range. The Emergency Department study implemented a Screening, Brief Intervention and Referral control condition, similar to the TAU condition planned in the current protocol, which yielded a rate of post-discharge buprenorphine maintenance treatment of 45%. We anticipate that the population recruited for this study will be among the most severely ill patients with OUD, being those requiring hospitalization for infections, and therefore we conservatively assume that the proportion of patients meeting our primary outcome (enrolled in MAT for OUD 12 weeks after hospital discharge) will be 40% in the TAU arm and 60% in ID/LAB arm. We have chosen a sample size of N = 200 total (N = 100 per study arm), in order to ensure sufficient power (power = 80%) with a two-sided level of significance of 5% to detect a difference of at least 19.7% between the TAU and ID/LAB treatment groups (i.e., 40% treatment enrollment in the TAU arm and at least 59.7% treatment enrollment in the ID/LAB arm). This rate difference of 19.7% is equivalent to an odds-ratio of 2.2 and would be clinically meaningful.

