Secondary outcomes: Statistical Models: For each of the secondary outcomes (see above) the effect of randomization to the ID/LAB arm compared to the TAU arm will be estimated with a model of the same general form as for the primary outcome (independent variables: treatment assignment (ID/LAB vs TAU), Site as a fixed effect, and baseline score as covariate where relevant) using logistic regression models (for binary outcomes), generalized linear model (for continuous outcomes), or longitudinal generalized mixed effects model (for longitudinal outcomes) with appropriate link functions (e.g. logit for binary outcomes). Longitudinal outcomes analyzed using a mixed effects models will utilize a generalized estimating equation with an autoregressive correlation structure (AR(1)) to account for within subject correlation over time, as well a random intercept accounting for between subject variability. In addition to site, covariates that are found to be related to the outcomes will be added to the models to improve the power for detecting significant differences.

Moderation and Mediation: Moderation Statistical Models: The effect of randomization to the ID/LAB vs TAU arms will be estimated for subpopulations based on the demographic and baseline characteristics selected as moderators (see above). We will estimate the moderation effect on primary outcome using a similar model to Aim 1 primary outcome with the inclusion of moderator by treatment interaction: $Y_i = \beta_0 + \beta_1 Trx_i + \beta_2 M_i + \beta_3 Trx_i M_i + \beta_4 C_i + s_i$ where M_i is the moderator status for i^{th} subject and Trx_i is subject's treatment assignment. Regardless of the significance of the interaction term, we will use the model to estimate the 95% confidence interval of the treatment effect for each level or category of the moderator variable, or the treatment effect at selected values of the moderator variable, if continuous. The moderator analyses are exploratory and hypothesis generating, but significant moderator effects can be useful in planning future efforts at implementation of medication treatment for opioid use disorder in medical settings by identifying subgroups that may particularly benefit. Identifying subgroups where there is less benefit may suggest future modifications to the implementation strategy to achieve better effect in those subgroups.

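### The primary logistic model takes in an open moderator list that the plan elsewhere treats as exploratory, and an outcome-driven covariate rule with no threshold also reaches it

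*Combined protocol and SAP*

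**What the plan says.** All the relevant text is in section 12.0 (Data Management).

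- **Primary outcome Statistical Model.** Week-12 enrollment is modelled by logistic regression on treatment, "with Site as a fixed effect, and covariates/moderators as listed above under" the Additional variables paragraph. The treatment odds ratio and its confidence limits are the effect estimate. Raw rates and rate differences are descriptive.
- **Additional variables.** The paragraph opens with "Covariates, primary and secondary analyses: Stratification factors" and makes site a fixed effect throughout. It then says: "In general, the baseline score for each outcome measure (where applicable) will be included as a covariate in outcome analyses". Moderators form a separate group: "A range of baseline moderator variables will be explored including" demographics, pain, fentanyl, other substance use, depression and "Type of infection (endocarditis/ osteomyelitis/bacteremia/ cellulitis/ etc". Both the list and its last item are open.
- **Significance Testing and Preliminary Analyses.** "Covariates associated with treatment outcome will be adjusted for in models used to test study hypotheses". No test, threshold, candidate pool or procedure follows, and the primary model is not exempted.
- **Secondary outcomes: Statistical Models.** The general form of the primary model is described as "independent variables: treatment assignment (ID/LAB vs TAU), Site as a fixed effect, and baseline score as covariate where relevant". For the secondary outcomes the paragraph then says: "In addition to site, covariates that are found to be related to the outcomes will be added to the models".
- **Moderation and Mediation.** Moderators enter separate interaction models, each moderator as its own term apart from the covariates, and these analyses are called exploratory.

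**The concern.** The primary-model paragraph puts into the confirmatory model a group of variables that two other paragraphs reserve for exploration. The list has no end, so the model has no fixed number of terms. Separately, the outcome-association rule covers any model that tests a study hypothesis, and the primary model is one. Which covariates enter would then depend on the outcome data and on a cut-off that nobody has written down.

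At stake are the headline odds ratio, its interval and, in a minority of trials, whether p falls below 0.05. The odds ratio is non-collapsible: its target value changes with the covariates held fixed, even when randomisation is perfect. A model with many slopes for about 100 events also pushes the estimate away from 1 through over-fitting. Two careful statisticians could follow the text and report different confirmatory results.

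**Working it through.** **1. The plan's own figure.** Inputs from the power analysis: 40% against 59.7%, 100 per arm, two-sided 5%. The two-proportion z-test with pooled variance under the null and no continuity correction gives 80.0% power. The odds ratio is (0.597/0.403)/(0.40/0.60) = 2.22, against the stated 2.2. Both reproduce. This calculation is for an unadjusted comparison, so it does not show which adjusted model was intended.

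**2. Size of the literal model.** Four demographic slopes (gender, age, ethnicity, living situation) + pain 1 + fentanyl 1 + other substance use 3 + depression 1 + infection type 4 (if five types) = 14. Ethnicity in four categories makes it 16. With treatment (1) and site (2), 14 becomes 17 slopes. Expected events are 40 + 59.7 = 99.7, so 99.7/17 = 5.9 per slope.

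**3. Simulation.** 5,000 trials per cell, N = 200, three sites of 67/67/66, permuted blocks of 4, and overall rates held at 40% and 59.7% (both 40% under the null). The following are assumptions, since the plan gives no figures for them:
- Site effects of +0.3/0/−0.3 log-odds.
- Prevalences: female 35%, Hispanic 12%, homeless 40%, fentanyl 70%, cannabis 40%, stimulant 50%, heavy drinking 20%, depression 50%, infection types 35/25/15/15/10%.
- Prognostic log-odds (absolute) for homelessness, stimulant, fentanyl and depression of 0 (none), 0.4 (moderate) or 0.7 (strong), with half that per SD for age and pain.
- Selection by univariate score test, with the Additional variables list as the candidate pool.

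Ranges cover 14 and 16 slopes, except that the selected-model odds ratios are the range over repeat runs with 14 slopes.

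| | None | Moderate | Strong |
|---|---|---|---|
| True conditional OR | 2.25 | 2.35 | 2.54 |
| Median OR, full list | 2.42–2.47 | 2.52–2.56 | 2.82–2.88 |
| Median OR, selected at p<0.05 | 2.26–2.28 | 2.32–2.33 | 2.49–2.55 |
| Verdict differs: full list vs treatment + site | about 6% | 7–8% | 8.5–9.6% |
| Verdict differs: selected (p<0.05) vs treatment + site | 2.0% | 4.5–4.6% | 7.2–7.6% |

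Selection at p<0.05 and at p<0.20 disagree with each other in about 3–4% of trials. Treatment plus site has a median OR of 2.28–2.29 with no prognostic variables.

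**4. Over-fitting separated from non-collapsibility.** Each full-list median is divided by its own true conditional OR:
- None: 2.42/2.25 = 1.08 to 2.47/2.25 = 1.10.
- Moderate: 2.52/2.35 = 1.07 to 2.56/2.35 = 1.09.
- Strong: 2.82/2.54 = 1.11 to 2.88/2.54 = 1.13.

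The excess is therefore about 7% to 13%. Repeat runs of 2,500 to 3,000 trials with 14 slopes gave mostly 8% to 12% (in the strong case 2.76/2.54 = 1.09 to 2.84/2.54 = 1.12). The rise in the target itself, from 2.25 to 2.54, is non-collapsibility and is not bias. For scale, the log-OR standard error is 0.32–0.35, and ln 1.07 = 0.07 to ln 1.13 = 0.12.

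**5. Type I error, one fixed model at a time.** Treatment + site 4.7–5.5%, full list 5.2–6.7%, selected 4.8–5.8% (5.0–6.0% in a repeat run at p<0.05).

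**The case against.** The strongest reply is that one reading reconciles the text. Additional variables separates site, covariates and moderators. The moderation paragraph makes moderators exploratory, and its equation carries the moderator as its own term. The word moderators in the primary-model paragraph is then a drafting slip. The largest figures above belong to that literal reading, while the selection rule shows no inflation at p<0.05. The plan also fixes the model family, site term, intention-to-treat set, alpha and missing-data rule, and it reports raw rates by arm. Finally, adjusting for prognostic covariates is legitimate and can add power.

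Most of this stands, and it limits the severity. But the slip sits in the one paragraph that defines the confirmatory model, and correcting it leaves the outcome-association rule in force with no threshold.

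Two stronger readings are tempting:
- A reader might infer three rival primary models, counting the form restated under the secondary outcomes as the third. The documents do not support this. That sentence gives a general form, with a baseline score only where relevant. No baseline score is defined for week-12 enrollment, so it reduces to treatment plus site, and it does not conflict with Additional variables or with the outcome-association rule.
- A reader might infer a false-positive rate of 8–10%. Simulation does give 7.8–9.8% when any of four or five readings may count as a success, but only if the best is picked after the results are seen. No passage provides for that.

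**Conclusion.** The point holds in a limited form. The confirmatory model names moderators that the plan elsewhere keeps exploratory, from a list with no end. A data-driven covariate rule with no threshold also reaches the primary test.

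The practical effect is modest. If the primary paragraph is followed literally, the odds ratio is overstated by about 7–13% relative to its own target, and the significance verdict differs from treatment plus site in about 6–10% of trials. If covariates are selected on outcome, the estimate is not inflated at p<0.05 and type I error is near nominal, but the verdict differs in about 2–8% of trials and depends slightly on the unstated cut-off. These sizes rest on the assumed prevalences, prognostic effects, site effects, infection categories and candidate pool. The textual conflict does not depend on them.

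Nothing here shows that the trial is too small: N = 200 and 80% power reproduce. The wording should be settled before outcomes by arm are seen.

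**What to change.** 1. Strike moderators from the primary-model paragraph and state the primary model as treatment plus site.
2. If baseline covariates are to be added, name them as a short closed list, fixed before outcomes by arm are seen.
3. For the primary outcome, use adjustment for outcome-associated covariates only as a labelled sensitivity analysis.
4. Keep moderators in the exploratory interaction models, as the moderation paragraph already does.

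The cost is SAP wording only, and N = 200 is unchanged. The downside is some power if strongly prognostic covariates are left out. Under the same assumptions, treatment plus site compared with the full list is 2 points higher with no prognostic variables and about equal with moderate ones. It is about 3 points lower with strong ones (82% vs 85%) and 11 lower with very strong ones (81% vs 92%, log-odds 1.4). A prespecified list of four recovers part of this: 84% (strong) and 88.5% (very strong) if all four are prognostic, but only 82–83% and 85% if two are.

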14.0 Withdrawal of Subjects (if applicable)

If the study team feels that the participant's condition is worsening, the team may terminate the participant's study treatment and institute a higher level of care, such as residential treatment or expedited initiation of medication for opioid use disorder. This is outlined in further detail in the DSMP.

As part of the informed consent process, participants will be informed that part of participation in the study means that the study team will track participants into the community who lose contact with the study team and miss appointments for research assessments, and what the tracking involves (e.g. contacting family members and other personal contacts that the participant has listed and given permission to be contacted, looking for the participant in the community in places where he/she is known to frequent). Participants will be informed that they can refuse to engage with study staff and/or ask for their study participation to end and tracking efforts will be discontinued. However, it is our experience from other treatment studies employing active tracking of this type that participants are often grateful for the effort to locate them and typically willing to engage/re-engage with the study team.

15.0 Risks to Subjects

As in all research studies, there are potential risks. We go to great efforts, however, to ensure that risks are minimized. This is particularly true as we intend to conduct this study with a vulnerable population. Moreover, there is an additional risk with this study, particularly since it initially involves research with those with substance use disorders. Within this section, we will first describe the individual risks associated with the interviews, followed by the laboratory testing, and other potential risks. There may be risks that are currently not known or have yet to be experienced by patients taking Sublocade®.

Risks Associated with Opioid Use Disorder: Opioid use disorder is a dangerous disorder associated with impaired functioning, morbidity (including infections of the type that participants in this protocol will be suffering from on admission), and mortality due to opioid overdose. Patients will be protected from opioid use while inpatient, but the risk of relapse is high after discharge from hospital unless the patient is maintained on one of the effective medications (methadone, buprenorphine, or extended-release naltrexone) which protect against relapse and overdose. Participation in the research study may mitigate these risks to the extent that patients in the ID/LAB arm are started and maintained on long-acting injection buprenorphine, and patients in TAU arm started on and successfully referred to ongoing medication treatment. This risk may differ between study arms to the extent that the ID/LAB arm is more successful at stabilizing patients on maintenance medication.

Risks Associated with Questionnaires: During the administration of questionnaires, topics such as alcohol and drug use, alcohol and drug treatment, mental health and questions regarding HIV risk behaviors will come up. These topics may make participants feel uncomfortable. Participants may choose not to answer all or any part of a question. Participant names will be recorded, but kept safe, according to HIPAA regulations. If the participant chooses to be screened for the study, minimal identifiable information will be collected to ensure eligibility. Consent procedures are explained above. If the potential participant agrees to consent, they will be asked to sign an IRB approved consent form on a tablet. Data from the questionnaires will be reviewed after they have been completed. No study-related unanticipated problems or adverse events are expected to occur in this part of the study. Hard copies of data collected will be stored in a locked cabinet, although we expect minimal to no paper copies. Electronic copies can be accessed by providing a user identification and password.

Risks Associated with HIV testing: Participants will receive verbal information about rapid HIV and HCV testing including a description of the rapid testing procedure, timing for and meaning of test results and explanation of the window period during which an HIV and HCV antibody test might be

negative. Providing this information takes less than 5 minutes. Participants will then be offered the OraQuick Rapid HIV-1/2 and OraQuick Rapid HCV Antibody Tests. The Research Assistants have been trained in how to perform these rapid tests. A reactive test will be followed by a confirmatory blood test. Participants who test positive will also receive emotional support and posttest counseling on sexual and injection drug use risk behavior and importance of ongoing HIV primary medical care and HCV treatments. They will be assisted in scheduling an appointment with an HIV provider. There will be at least one practicing Infectious Disease physician at each site to provide any requisite oversight for testing and referrals.

In accordance with CT, PA and SC state laws, any new HIV and HCV test results must be reported and this will be outlined in each consent form. We have operated routine HIV and HCV testing for study participants for decades and have extensive experience not only complying with state laws for HIV testing, but with post-test counseling and ensuring engagement in HIV care if indicated. All results will be kept confidential.

Risks Associated with Loss of Confidentiality: As with all research, there is a risk that involves potential breaches of confidentiality. We intend to do everything possible to reduce this risk and this is one of the process measures we propose to measure. Participants with substance and alcohol use disorders are a vulnerable population. Thus, our research to date has insured strict confidentiality safeguards.

Potential sites for breaches of confidentiality include during the recruitment process at the hospital, during study interviews, or from data management systems. From our research efforts and provision of clinical care for out-of-treatment drug users, HCV-infected and HIV infected drug users in clinical settings, we have paid careful attention to potential breaches of confidentiality for subjects undergoing interviews. All information is stored in password-protected, encrypted computers with double-password protection for opening specified files. All confidential information (study instruments, laboratory results, etc.) will be recorded with study participant number only and maintained in locked cabinets within offices at each study site; data will only be available to be opened by the Project Coordinator, Data Manager, co-Principal Investigators, and Statistician. Electronic databases will be maintained through password-protected computers and files and maintained at the Columbia Department of Biostatistics.

Risks associated with long-acting injectable buprenorphine (LAB):

Risks of LAB (Sublocade®) include: increased opioid withdrawal symptoms if the medication is initiated too soon after last opioid dose;

Side effects related to subcutaneous injection: pain, inflammation, or (rarely) infection at the injection site. There have been some reports of severe injection-site reactions causing abscess, ulceration, and necrosis, in some cases requiring surgical depot removal, debridement, antibiotic administration;

Side effects related to opioids: nausea, constipation, sedation, respiratory depression (particularly when combined with alcohol or other sedating drugs). Opioid use disorder could worsen if the Sublocade® does not prove effective or is discontinued by the patient, including functional impairment as well as risk of death from drug overdose.

Risks associated with Treatment as Usual (TAU): The main risks associated with TAU include: opioid withdrawal symptoms during detoxification; worsening of opioid use disorder, including functional impairment as well as risk of death from drug overdose.

Risks associated with drawing blood include momentary discomfort and/or bruising. Infection, excess bleeding, clotting, or fainting is possible, although unlikely.

Risks associated with pregnancy: If a participant becomes pregnant and tests positive for illegal drugs, it is a law that the South Carolina Department of Social Services (DSS) must be notified.

Participants could be ordered to mandatory drug treatment, lose custody of their children, or be jailed. We will mitigate these risks by performing all pregnancy tests before tests for illegal substances, and by making clear in the consent form these reporting requirements. A person who is found to be pregnant will be withdrawn from the study and no further urine toxicology testing or questions regarding drug use will be queried; they will subsequently be referred to care for both pregnancy and addition. There are no such reporting requirements in Pennsylvania and Connecticut.

Psychiatric Risks:

If someone has a potential new psychiatric diagnosis via any of the structured questionnaires, a study doctor will be notified within 48 hours of the assessment. The participant will be linked for an evaluation and care with a clinician from a designated Psychiatric Team at each site. Participants with existing psychiatric diagnoses will continue their treatments as usual.

If someone is actively suicidal (which can be determined by participant self-report, the PHQ suicidality question OR the MINI suicidality section), each site will follow the general protocol below:

1. If the research staff member is uncomfortable and there is a more experienced clinician available, they will request their assistance. If assistance is not available or the client reports imminent intent to harm self or others, the study staff member will:

If the participant is currently hospitalized, a referral will be made to inpatient psychiatry.

If participant is not hospitalized, we will use the following protocol:

 - a. Have a co-worker call 911
 - b. Stay with participant, not leave participant alone
 - c. Escort participant to ambulance and provide all necessary information
 - d. Notify study doctor, who will plan a psychiatric team consultation for participant
2. If a participant is not in an imminent danger to him/her self or others:
 - a. If the participant is currently hospitalized, a referral will be made to inpatient psychiatry.
 - b. If participant is not hospitalized, give client telephone numbers for crisis counseling, emergency room, or local mental health association
 - c. A study staff member will follow up with the participant within 24 hours
 - d. Notify study doctor, who will plan a psychiatric team consultation for participant

